2.5 Hypothesis testing

All tests will be conducted with a nominal significance level of $\alpha = 0.05$ (two-sided).

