superiority criteria for both influenza A strains ( $>1.5$  GMT ratio), and the responses for influenza B met non-inferiority criteria. For all strains, seroprotection rates were higher in those individuals who received HD-TIV than in those who received standard dose TIV. Local reactions were more frequent in individuals who received HD-TIV, but the reactions were mild to moderate. The superiority of immune responses to influenza A antigens in the HD-TIV, compared to the standard-dose group, in this phase III trial led to the licensure of HD-TIV in individuals  $\geq 65$  years. In addition, not only does the HD-TIV induced significantly higher antibody responses in this population, it provided better protection (relative efficacy, 24.2%) against laboratory-confirmed influenza illness compared to standard dose TIV.

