### 4. Prior Experience with HD-TIV in the Immunocompromised Subjects:

**a. Adult HSCT Recipients.** This single-center, randomized, double-blind, phase I safety and immunogenicity trial, conducted at Vanderbilt University, compared HD to standard dose TIV in adult allogeneic HSCT

recipients, not on immunosuppressive therapy for treatment of active GVHD, and at least 6 months post-transplant. Subjects were randomized in a 2:1 fashion to receive 2010-11 or 2011-12 TIV HD-TIV or standard dose TIV. Forty-four subjects were enrolled (19 in year 1 and 25 in year 2) at a median of 7.9 months after allogeneic HSCT, median age of 50.1 years, 61% male, and 100% white, and 29 HD and 15 SD subjects. HD group had higher median IgG level (676 vs. 469, p=0.025). The HD group reported more local symptoms compared to standard dose. No serious adverse events (SAEs) were attributed to the vaccine, and no differences in systemic reactions were noted. The HD group had a higher percentage of individuals with a HAI titer  $\geq 1:40$  to H3N2 after HD-TIV, (81% versus 36%, p=0.004) and higher GMT [207.9 versus 30.3, 177.6 95% CI difference, (63.5 - 401.8)], with GMT ratio 6.9. These results are published in *Biology of Blood and Marrow Transplant*.

**b. Pediatric Solid Organ Transplant (SOT) Recipients.** This multi-center, randomized, double-blind, phase I safety and immunogenicity trial, conducted at Vanderbilt and the Children's Hospital of Pittsburgh during the 2011-12 influenza season, compared HD to standard dose TIV in pediatric SOT patients. Enrollees were 3-17 years of age and at least 6 months post-transplant. The mean age was 11.25 years, 68% were male, transplanted organs were 45% renal, 26% heart, 21% liver, 5% lung, and 5% intestinal, with median of 2.2 years since transplant. Twenty-three subjects were given HD and 15 were given standard dose TIV. No individuals had rejection associated with vaccination. Fatigue and body ache were greater in the HD group compared to the standard dose group, but no differences in local reactions were noted. Subjects in the HD group had a higher percentage of a 4-fold rise to H3N2 compared to the standard dose group (56% versus 13%, p=0.08). These results were published in *Pediatric Transplantation*.

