**c. Pediatric Acute Lymphoblastic Leukemia (ALL) Subjects.** This single-center, randomized, double-blind, phase I safety and immunogenicity trial was conducted at Vanderbilt University, comparing HD to standard dose TIV in children 3-17 years of age with ALL. Fifty subjects were enrolled (20 in year 1 and 30 in year 2), with a mean age of 8.25 years, 62% were male, and 78% were receiving maintenance therapy. Thirty-four subjects were given HD and 16 were given standard dose. Safety data revealed no differences between the groups for total solicited systemic and local reactions; however, the standard dose group reported more fatigue and headache. No SAEs were attributed to vaccination. The immune response, measured by a  $\geq 4$ -fold rise in HAI titer, was similar for each vaccine antigen in both groups; however, descriptive data in ALL recipients comparing specific B-cell immune response to each antigen suggest better responses with HD-TIV (unpublished data, [name] laboratory, St. Jude, Memphis, TN). The main results are published in *Pediatric Blood Cancer*.

**5. Inclusion of Quadrivalent Inactivated Influenza Vaccine (QIV).** Although two influenza B lineages have been co-circulating since the 1980s, TIV contains only one B strain, which provides little-to-no protection against the alternate B-lineage strain; however, about 70% of recent B viruses have been antigenically related to the B virus component of the trivalent flu vaccines. A standard-dose QIV is currently available and provides additional protection against the second B strain while retaining non-inferior immunogenicity to the other 3 TIV strains. High dose QIV will not be available for the upcoming influenza season (*personal communication with Sanofi Pasteur*). This study will be the first to evaluate standard dose QIV and HD-TIV in this population.

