## Comparison of High vs. Standard Dose Flu Vaccine in Pediatric Stem Cell Transplant Recipients

DMID Protocol Number 16-0117

Protocol Version 8.0

Date: 9/12/2019

Since the majority of influenza illness is due to influenza A and HD-TIV licensure was based on influenza A antigen responses, the results of these studies could be generalizable to HD-QIV, should it become commercially available in the future. In addition, influenza B antigens have lower HAI titers compared to influenza A antigens, especially in children, including those without co-morbidities. Therefore, if the results from this trial reveal superior HAI titers to influenza A antigens, a HD-QIV vs. standard-dose QIV trial will not be necessary. Moreover, this study has significant potential to impact clinical practice in pediatric HSCT patients. Demonstration of safety and greater immunogenicity of HD-TIV versus standard dose QIV in this population could alter current influenza vaccine recommendations. Additionally, successful use of HD-TIV to enhance influenza-specific immune responses in pediatric HSCT patients could reduce influenza disease burden, morbidity, and mortality in these high-risk patients.

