1.2 Study objectives

Immunogenicity and safety objectives are organized into subsections below. To avoid repetitive language, *all* objectives apply to the target study population (namely, pediatric HSCT recipients).

1.2.1 *Objectives for HAI immunogenicity outcomes*

The primary objective is to determine whether two doses of HD-TIV is associated with a higher geometric mean HAI titer to either influenza A antigen (H1N1 and H3N2, evaluated separately) compared to two doses of SD-QIV.

The secondary objectives pertaining to HAI immunogenicity outcomes are as follows:

- To determine whether two doses of HD-TIV is associated with a higher geometric mean HAI titer to influenza B antigens as compared to two doses of SD-QIV.
- To determine whether two doses of HD-TIV is associated with higher odds of seroconversion or seroprotection in *any* HAI antigen as compared to two doses of SD-QIV.
- To compare HAI immunogenicity for each antigen between the following groups: (a) one dose of HD-TIV vs. one dose of SD-QIV, (b) one dose of HD-TIV vs. two doses of HD-TIV, and (c) one dose of SD-QIV vs. two doses of SD-QIV.

The tertiary objectives pertaining to HAI immunogenicity outcomes are as follows:

- To compare HAI immunogenicity for each antigen between the one dose of HD-TIV and two doses of SD-QIV.
- To determine whether time post-transplant, subject age, or GVHD status (presence/absence) modifies the association between vaccination group and HAI response.
- To characterize the relationship between HAI titers, ex-vivo T and B cell phenotype, and ex-vivo influenza-specific T and B cell response in subjects receiving either HD-TIV or SD-QIV.
- To compare HAI immunogenicity outcomes between treatment groups (one dose or two doses of HD-TIV vs. one dose or two doses of SD-QIV, respectively) among those enrolled for a second year (repeaters).

1.2.2 *Objectives for safety outcomes*

The primary objectives for safety outcomes are to compare the frequency/severity of solicited local injection site adverse events (AEs) and systemic AEs between HD-TIV and SD-QIV following the first dose and following the second dose. The secondary objective is to compare safety outcomes between treatment groups among those enrolled for a second consecutive year (repeaters).

1.2.3 *Further exploratory objectives*

- To compare the persistence of HAI and microneutralization (MN) titers between HD-TIV and SD-QIV across all four antigens seven months after the final vaccine dose.

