5.1 Analysis of continuous HAI titer responses

We will use mixed effect models to analyze continuous titers. All comparisons will be made on the geometric mean ratio scale. Consider the following model form:

$$\log(Y_{it}) = \beta_0 + \beta_1 \mathbf{1}(X = 1) + \beta_2 \mathbf{1}(t = 3) + \beta_3 \mathbf{1}(t = 3; X = 1) + \boldsymbol{\beta}_L \mathbf{L} + \gamma_i + \gamma_S + \varepsilon_{it},$$

under which all primary and secondary aims pertaining to continuous HAI titer outcomes can be addressed. The parameters of this model and the comparisons to which they correspond are summarized in Table 3.

Any continuous variables (e.g., time post-transplant and log-transformed baseline titer) used for adjustment will be flexibly modeled using natural cubic splines with knots at the 25th, 50th, and 75th percentiles.

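### The SAP's primary HAI objective asks for a higher titer to either influenza A strain but sets no success or multiplicity rule, so an either-strain claim would exceed the false-win rate of one test

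*SAP*

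**What the plan says.** SAP 1.2.1 gives one primary objective for HAI immunogenicity: whether two doses of HD-TIV are associated with a "higher geometric mean HAI titer to either influenza A antigen (H1N1 and H3N2, evaluated separately) compared to two doses of SD-QIV". SAP 2.5 consists of one sentence: "All tests will be conducted with a nominal significance level of $\alpha = 0.05$ (two-sided").

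SAP 5.1 sets out one mixed model form "under which all primary and secondary aims pertaining to continuous HAI titer outcomes can be addressed". Table 3 labels one contrast as primary, the two-dose comparison at visit 3, and does not mention that it will be tested for two strains.

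Neither document contains a both-strains requirement, an order of testing, an alpha split, or a statement of what result meets the objective. Protocol section C.17 cannot fill the gap: its immunogenicity analysis uses Bayesian posterior distributions and credible intervals, and it sets no error rate. The protocol's sample size concerns seroprotection to at least one antigen, not the SAP's titer endpoint.

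SAP 1.2.2 names primary objectives for safety as well. They are separate and are not counted here.

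**The concern.** One objective is tied to two tests by the word *either*. On its ordinary reading, a significant result for H1N1 alone or for H3N2 alone would meet it. Each test has its own 0.05 level, so the chance that at least one falsely favors HD-TIV is larger than for a single test.

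At stake is what may be claimed from a split result. If HD-TIV is higher for one strain and not the other, the SAP does not say whether the primary objective was met. That choice would then be made with the data in view. SAP 1.3 places the unblinded analyses after the SAP is final, so the rule can still be fixed in advance.

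**Working it through.** **Inputs.** Two tests, H1N1 and H3N2 (SAP 1.2.1). Two-sided 0.05 each (SAP 2.5). The correlation ρ between the two test statistics is not in the documents, so it is assumed at 0, 0.5, 0.7 and 0.9. The statistics are taken as bivariate normal, and each test is taken to have its true nominal size. The plan states no family-wise figure to reproduce.

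**Benchmark.** One two-sided 0.05 test falsely favors HD-TIV with probability 0.05/2 = 2.5%.

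**As planned, c = 1.960.**
- False HD-TIV win on at least one strain: 1 − P(Z1 < c, Z2 < c). At ρ = 0 this is 1 − 0.975² = 4.94%. Under any dependence it is at most 2 × 0.025 = 5.0%.
- Two-sided family-wise error: 1 − P(|Z1| < c, |Z2| < c). At ρ = 0 this is 1 − 0.95² = 9.75%. Under any dependence it is at most 2 × 0.05 = 10%.

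**With Holm, first-step bound c2 = 2.241 (two-sided 0.025).**
- Two-sided family-wise error: 1 − P(|Z1| < c2, |Z2| < c2). At ρ = 0 this is 1 − 0.975² = 4.94%.
- False HD-TIV win: 1 − P(Z1 < c2, Z2 < c2), plus the case where a false SD-QIV win at step one opens the second test at 0.05. At ρ = 0 this is (1 − 0.9875²) + 2 × 0.0125 × 0.0125 = 2.484% + 0.031% = 2.52%. The second term is negligible at ρ = 0.5 and above.

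Results by numerical integration:

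| ρ | False HD-TIV win, as planned | False HD-TIV win, Holm | Two-sided, as planned | Two-sided, Holm |
|---|---|---|---|---|
| 0 | 4.94% | 2.52% | 9.75% | 4.94% |
| 0.5 | 4.54% | 2.32% | 9.07% | 4.65% |
| 0.7 | 4.17% | 2.15% | 8.35% | 4.30% |
| 0.9 | 3.52% | 1.81% | 7.04% | 3.62% |

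The objective is directional, so the false HD-TIV win is the figure that matters. Relative to one test it is 4.94/2.5 = 1.98 times as large at ρ = 0 and 3.52/2.5 = 1.41 times at ρ = 0.9.

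**Power cost of Holm, illustrative.** The documents give no standard deviation or target ratio for the titers, so 80% unadjusted power per strain is assumed (mean shift 1.960 + 0.842 = 2.802).
- Only one strain has an effect: step one gives P(Z > 2.241 − 2.802) = 71.2%. Adding step two gives 71.45% at ρ = 0 and less at higher ρ.
- Both strains have effects, at ρ = 0: at least one win falls from 1 − 0.20² = 96% to 1 − (1 − 0.712)² = 92%. Wins on both fall from 0.80² = 64% to 0.64 − (0.80 − 0.712)² = 63%.

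| ρ | At least one win, unadjusted | At least one win, Holm | Both, unadjusted | Both, Holm |
|---|---|---|---|---|
| 0 | 96% | 92% | 64% | 63% |
| 0.5 | 91% | 85% | 69% | 68% |
| 0.7 | 89% | 82% | 71% | 70% |
| 0.9 | 85% | 77% | 75% | 73% |

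**The case against.** The strongest reply is that the SAP intends strain-by-strain conclusions. It says the two antigens are evaluated separately, it calls its level nominal, and this is a phase II trial. On that reading each conclusion has its own 5% level and no claim is inflated. If both strains were required, there would be no inflation either. This stands as far as it goes: the excess error arises only if one strain is enough. It does not remove the gap, because the objective still says *either* and no rule says what meets it.

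Four stronger readings are tempting, and the documents do not support them.

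- **That the SAP contradicts itself.** It promises no family-wise 5%, so nothing is contradicted.
- **That an either-strain claim has no error control, or a false-win rate near 10%.** The false HD-TIV win cannot exceed 5.0%. About half of the two-sided figure is false SD-QIV wins, which could not meet a directional objective.
- **That a one-strain win would settle the later HD-QIV question.** Protocol B.6 says "if the results from this trial reveal superior HAI titers to influenza A antigens, a HD-QIV vs. standard-dose QIV trial will not be necessary". It speaks of antigens in the plural and does not say what a one-strain result would mean.
- **That a one-strain result is likely.** The prior trials in protocol B.3 and B.4 do not establish this. The pediatric solid organ trial reports an H3N2 difference with p=0.08 and no H1N1 result, the leukemia trial's 4-fold rise "was similar for each vaccine antigen in both groups", and the phase III trial in the elderly met "superiority criteria for both influenza A strains".

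**Conclusion.** The point holds in conditional form and is a low-cost improvement that should be made. The missing success and multiplicity rule is a matter of record. The size of the problem depends on one strain being accepted as meeting the primary HAI objective. In that case the false HD-TIV win lies between 4.94% and 3.52% over the assumed correlations of 0 to 0.9, instead of 2.5%. The two-test family excludes the primary safety comparisons.

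**What to change.** Choose one of two routes before unblinding.

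1. **If one strain is enough,** add to SAP 2.5: *The primary HAI objective is met if the primary visit-3 HD-TIV vs SD-QIV geometric mean titer ratio is significantly above 1 for H1N1 or for H3N2. The two tests are controlled at a two-sided family-wise 0.05 by Holm: the smaller p-value is tested at 0.025 and, only if it is rejected, the other at 0.05.*
2. **If per-antigen inference is meant,** replace *either* with *each* in 1.2.1, state that error is controlled per antigen only, always report both strains, and make no either-strain claim.

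Do not name a model parameter in the new sentence unless Table 3 is reconciled at the same time. Table 3 lists β3 as the primary parameter, whereas the visit-3 group difference in the 5.1 model is β1 + β3. That is a separate issue.

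**Cost.** Neither route needs extra participants. The first takes two sentences and, under the illustrative 80%, lowers power to about 71% if only one strain has an effect. If both do, the chance of at least one win falls from 96–85% to 92–77%. The second costs no power but gives up the either-strain claim.

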2.6 Outliers

Outliers will be identified during the data management and data analysis process for the purposes of error detection and reconciliation; all data deemed to be accurate will be included in the analyses. Sensitivity analyses may be performed to evaluate the impact of outliers.

2.7 Data transformations and lower limits of detection

Laboratory data (in particular, HAI titer values) with clearly defined lower and upper limits of detection (L and U, respectively) will be handled as follows:

1. Observations not meeting the lower limit of detection will be given a value of half the lower limit of detection [e.g., those not responding to a titer of 1:L will be given a titer of 1:(L/2)].
2. Observations meeting the upper limit of detection will be given a value of the upper limit of detection (e.g., those responding to a titer of 1:U will be given a titer of 1:U) in the primary analysis. A range of subsequent sensitivity analyses will be conducted to evaluate sensitivity to departures from this convention.

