## 2. Prior Influenza Vaccine Trials in HSCT Recipients:

Influenza vaccination is the primary mode for prevention of influenza infection. Protection is primarily mediated by virus-specific antibodies that depend on an intact humoral response. Both B cell and T cells responses are impaired in HSCT recipients, functional recovery of B and T lymphocytes can take up to 2 years or even longer. Limited data are available regarding influenza vaccine responses in pediatric HSCT recipients because the majority of influenza vaccine trials have been conducted in adult HSCT recipients. Only 5 of these trials included children, and only one exclusively included children, with total enrollment of 5 subjects. Therefore, dedicated influenza vaccine trials in pediatric HSCT patients are needed.

Despite limited clinical data for influenza vaccine efficacy in this population, yearly vaccination is recommended, beginning 3-6 months after HSCT. However, the optimal post-transplantation vaccine schedule has not been established. Existing data for influenza vaccination in HSCT recipients are primarily from subjects who received influenza vaccination between 6 months and 3 years after HSCT. Thus, little data exist to support vaccinating pediatric HSCT recipients earlier than 6 months or later than 3 years post-transplant. The percentage of HSCT recipients that achieve seroprotective hemagglutinin inhibition (HAI) titers (defined as  $\geq 1:40$ ) one month after standard influenza vaccination is very low when compared to healthy controls. While this impaired vaccine-induced immune response is likely due to incomplete immune reconstitution or immunosuppressive therapies, the exact immune mechanisms of HSCT recipients' poor response to influenza vaccination are not well described. Notably, graft versus host disease (GVHD), low number of CD19+ B cells, and earlier timing of vaccination post-transplant have been implicated as factors associated with lower titers after influenza vaccine.

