### **15. Laboratory Procedures:**

- a. **Specimen Preparation, Handling, and Shipping:** Blood will be collected from a vein or from a central line from subjects. Study personnel or clinical research staff will collect the blood samples, label without personal identifiers, and deliver to the laboratory for preparation of serum and freezing of the sera until further testing and/or shipment to Sanofi laboratory for HAI and MN testing and B and T cell influenza-specific testing at Vanderbilt. Other clinical labs will be sent the local lab.
- b. **Hemagglutination Inhibition Assays (HAI):** Sera will be shipped to **Sanofi** laboratory for HAI testing. Sera will be initially diluted 1:10 per protocol. Pre-vaccination and post-vaccination sera will be analyzed simultaneously to minimize variability in the HAI assay. HAI titers will be determined for each influenza antigen included in QIV 2016-2017 or 2017-2018 or 2018-2019.
- c. **Neuraminidase Inhibition Assays (NAI):** Sera will be shipped to Vanderbilt for NAI testing and results will be compared to HAI. NAI testing will be done at [name] lab in Mt. Sinai.
- d. **Microneutralization assays:** Sera will be shipped to **Sanofi** laboratory for MN testing and results will be compared to HAI.
- e. **Influenza-specific B and T cell Responses and Immunophenotyping of B and T cells:** Samples will be collected at baseline, 5-10 days (optional) and 28-42 days after each vaccination and 180 days ( $\pm$ 42 days) after second vaccination. After ficoll separation, peripheral blood mononuclear cells (PBMC) will be cryopreserved for future analysis. Each site will do this locally and the off-sites will ship to **[name]** laboratory at Vanderbilt in Nashville, TN. This will ensure all time points from each individual can be evaluated simultaneously. We propose to study B and T cell responses to vaccination with mass cytometry technology (CyTOF), and functional assays such as *in-vitro* IL-21 production in response to vaccine antigen.
- f. **Nasal swabs:** a nasal swab will be collected by either using viral transport media or using PrimeStore MTM, which can be stored at room temperature until ready for shipment to Vanderbilt in Nashville, TN for PCR testing for influenza.

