## **17. Statistical Considerations:**

- a. **Sample Size Calculations:** A total of 200 children will be targeted, with 100 in each group. This is based on the assumption, with 80% power, that 20% of the children in the standard dose group will achieve a protective titer compared to 40% of the HD-TIV group for at least one influenza antigen. Accounting for a 20% drop out rate, 100 children in each group will be needed.

Strain	Expected Seroprotection HD-TIV	Expected Seroprotection standard dose	N (HD)	N (SD)	Power	Total N with 20% drop out
Expected HD-TIV seroprotection is twice as of standard dose						
A	40%	20%	80	80	80%	200
A	50%	25%	55	55	80%	138
A	60%	30%	40	40	80%	100
A	70%	35%	28	28	80%	70

- b. **Immunogenicity analysis:** The probability of achieving a 4-fold (or greater) rise in post-vaccination HAI titers relative to baseline, as well as the probability of a HAI titer greater than

1:40, will be estimated using a binomial model. We will calculate the Bayesian posterior distribution of the probabilities under all 4 combinations of standard and HD-TIV crossed with a single dose and two doses. From these probabilities, odds ratios will be calculated along with 95% credible intervals. These quantities will be modeled as a logit-linear function of several covariates, including CD4+/CD8+/CD19+ and IgG levels, absolute neutrophil and lymphocyte count (or their ratio), time from post-transplant to enrollment, type of preparative regimen, donor status, and stem cell source. In addition, the distributions of geometric mean HAI titers for high and standard dose recipients will be estimated via log-normal models and expressed as ratios in order to evaluate the evidence for higher GMT in the HD-TIV sample, after one and two vaccines. In addition, we will compare each group to document if they meet serological criteria by WHO biological standards for influenza vaccines (>40% for seroconversion, GMT >2.5-fold increase, and >70% with  $\geq 1:40$ ).

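### Does setting titers below the detection limit to half that limit, with no explicit lower-limit sensitivity analysis, undermine the primary geometric mean ratio?

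*SAP*

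**What the plan says.** SAP 2.7, whose heading names the lower limits of detection, has two numbered items. Item 1 reads "Observations not meeting the lower limit of detection will be given a value of half the lower limit of detection" and adds only an example. Item 2 keeps readings at the upper limit at that limit in the primary analysis and ends: "A range of subsequent sensitivity analyses will be conducted to evaluate sensitivity to departures from this convention".

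The primary objective in SAP 1.2.1 is "to determine whether two doses of HD-TIV is associated with a higher geometric mean HAI titer to either influenza A antigen". SAP 5.1 fits a linear mixed model to log titer without a censoring term and states: "All comparisons will be made on the geometric mean ratio scale".

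Neither document gives L as a number. Protocol C.15.b says "Sera will be initially diluted 1:10 per protocol", which suggests L = 1:10. Neither gives an expected share of readings below L or a standard deviation of log titer.

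**The concern.** By position, and because it speaks of one convention, the sensitivity sentence attaches most naturally to the upper limit. The lower-limit rule then has no stated check. Multiple imputation (SAP 2.3) addresses missing values, robust standard errors (2.4) leave the substituted value as it is, and the outlier checks (2.6) are optional and concern something else.

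Low titers are also the likelier problem in this population. Protocol B.2 notes "Both B cell and T cells responses are impaired in HSCT recipients", and Protocol C.17.a plans on the assumption that "20% of the children in the standard dose group will achieve a protective titer", for at least one antigen. If a large share of SD-QIV children and a smaller share of HD-TIV children read below L, the size of the primary GMR and its confidence interval would rest partly on a conventional number, and the report might not show by how much.

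**Working it through.** **Inputs.** From the documents: the L/2 rule (SAP 2.7), the GMR scale (SAP 5.1), the 1:10 starting dilution (Protocol C.15.b), 20% versus 40% at or above 1:40 with 80 evaluable per arm (Protocol C.17.a), and the adult H3N2 result (Protocol B.4.a), "81% versus 36%, p=0.004) and higher GMT [207.9 versus 30.3". Assumed: L = 1:10, log-normal titers, and the spreads below. The comparison is HD-TIV versus SD-QIV at visit 3, without covariates.

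**1. The plan's own figures.** Sample size: (1.96 + 0.84)² × (0.4×0.6 + 0.2×0.8) / 0.2² gives 79 per arm, against 80 stated; 80/0.8 = 100 per arm. Adult ratio: 207.9/30.3 = 6.9, as stated. Both reproduce.

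**2. Exact effect of the substituted value.** An arm's mean log titer is the contribution of its detected readings plus p × log(c), where p is the share below L and c the substituted value. Changing c from L/2 to c′ multiplies the GMR by (c′/(L/2))^(pHD − pSD). No distribution below L is needed.

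| pHD − pSD | L instead of L/2 | L/4 instead of L/2 |
|---|---|---|
| 0 | ×1.00 | ×1.00 |
| −0.023 | ×0.984 | ×1.016 |
| −0.10 | ×0.933 | ×1.072 |
| −0.20 | ×0.871 | ×1.149 |

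Assigning L is an extreme bound, because it gives a non-detect the same titer as a serum that does react at 1:L.

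**3. The only titer data in the documents.** With log-normal titers, the log10 standard deviation is (log10 40 − log10 GMT)/z, with z the normal quantile of the share below 1:40.
- Standard dose: (1.602 − 1.481)/0.358 = 0.34. Share below 1:10: Φ((1 − 1.481)/0.34) = 7.6%.
- High dose: (1.602 − 2.318)/(−0.878) = 0.82. Share below 1:10: Φ((1 − 2.318)/0.82) = 5.3%.

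The gap is 2.3 points. L/2 substitution moves the ratio from 6.9 to 7.0-7.1. These are 44 adults and one antigen, and the published means may already contain substituted values.

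**4. Assumed spreads.** SD-QIV has 20% at or above 1:40, the true GMR is 2.0, there are 80 per arm, and titers are continuous.

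| log10 standard deviation | Below 1:10, SD-QIV / HD-TIV | GMR with L/2 | 95% CI coverage |
|---|---|---|---|
| 0.34 | 18% / 4% | 2.07 | 94-95% |
| 0.4 | 25% / 8% | 2.03 | 95% |
| 0.5 | 36% / 17% | 1.91 | 94% |
| 0.6 | 44% / 25% | 1.79 | 91% |
| 0.7 | 49% / 33% | 1.69 | 87% |

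At 0.4, non-detects are common and uneven, yet the bias is negligible. At 0.6 and 0.7 the ratio is understated, which works against HD-TIV rather than for it.

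Flooring detected titers to two-fold steps lowers the GMR at 0.5 to 1.78. Reading them at mid-step, with L/2 unchanged, gives 1.90. That further loss comes from how detected titers are read, not from the L/2 rule.

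**5. Effect on the conclusion.** A separate simulation fixed 20% and 40% at or above 1:40, used two-fold readings, and took a standard deviation of ln titer from 1.0 to 2.0 (29-56% of SD-QIV and 13-33% of HD-TIV below L). Power was 0.92-0.94 with L/2 and 0.89-0.92 with L. The test result differed across L/4, L/2, L/√2 and L in about 5-6% of trials.

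**6. Is a censored model better?** Suppose true non-responders sit at 1:5 (40% of SD-QIV, 20% of HD-TIV), and responders have a GMT of 30 and a log10 standard deviation of 0.35 in both arms. The constructed GMR is (30/5)^(0.4 − 0.2) = 6^0.2 = 1.43. L/2 with continuous titers gives 1.42. An interval-censored normal fit gives 1.51 with a common standard deviation and 1.64 with separate ones. The censored fit recovers the true ratio only when the tail below L has the shape it assumes.

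**The case for a change.** The strongest case for a change is that impaired responders are exactly where readings below L should pile up, while the explicit check is at the other end of the scale. The multiplier in step 2 needs no distributional assumption. Under the planning rates in step 5, moving from L/2 to L lowers the GMR by 11-15%, and moving to L/4 raises it by 12-17%. The share below L cannot be settled from the documents, and the 20% planning rate is for at least one antigen, so a single antigen could do worse. A sentence added before unblinding costs little, whereas a check added afterwards might look data-driven.

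Much of this stands. Upper limit only is the more natural reading of SAP 2.7, the reported size of the ratio can move, and coverage falls to 91% and 87% in the two widest scenarios of step 4. It does not follow that the plan must change. The material cases depend on an assumed spread and L, and those in step 4 also on an assumed true ratio; the one data set available points the other way. The sentence closing SAP 2.7 can be read as covering both limits, so running it at the lower end would not be an invention. Half the limit would remain the primary rule under any version of the proposal.

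**Conclusion.** The concern describes the text fairly but does not justify a change. Following SAP 2.7 as written answers the primary question, whether HD-TIV gives a higher geometric mean titer, by a conventional rule. The direction does not depend on the substituted value in any scenario examined, the significance result rarely does, and seroprotection at 1:40 does not use it.

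What can move is the size of the GMR: under 2% on the gap implied by the adult data, about 7% for a 10-point gap, and more only if non-detects are both common and clearly uneven. These figures assume L = 1:10 and an unadjusted two-arm comparison. With adjustment for baseline titer, itself subject to L/2, they would differ somewhat.

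The remainder is missing detail that analysts fill sensibly: the numerical limits, the share below L by arm, visit and antigen, and the same kind of alternative values at the lower limit as at the upper. A censored model could be one more sensitivity run. It rests on a tail that the data cannot check, so it is not a better primary method.
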